The use of temsirolimus is likely to result in increases in serum glucose. In the phase 3 trial, 89% of patients receiving temsirolimus had at least one elevated serum glucose while on treatment, and 26% of patients reported hyperglycemia as an adverse event. This may result in the need for an increase in the dose of, or initiation of, insulin and/or oral hypoglycemic agent therapy. Serum glucose should be tested before and during treatment with temsirolimus. Patients should be advised to report excessive thirst or any increase in the volume or frequency of urination.

Infections

The use of temsirolimus may result in immunosuppression. Patients should be carefully observed for the occurrence of infections, including opportunistic infections

Interstitial Lung Disease

Cases of interstitial lung disease, some resulting in death, occurred in patients who received temsirolimus. Some patients were asymptomatic with infiltrates detected on computed tomography scan or chest radiograph. Others presented with symptoms such as dyspnea, cough, hypoxia, and fever. Some patients required discontinuation of temsirolimus and/or treatment with corticosteroids and/or antibiotics, while some patients continued treatment without additional intervention. Patients should be advised to report promptly any new or worsening respiratory symptoms.

Hyperlipemia

The use of temsirolimus is likely to result in increases in serum triglycerides and cholesterol. In the phase 3 trial, 87% of patients receiving temsirolimus had at least one elevated serum cholesterol value and 83% had at least one elevated serum triglyceride value. This may require initiation, or increase in the dose, of lipid-lowering agents. Serum cholesterol and triglycerides should be tested before and during treatment with temsirolimus.

Bowel Perforation

Cases of fatal bowel perforation occurred in patients who received temsirolimus. These patients presented with fever, abdominal pain, metabolic acidosis, bloody stools, diarrhea, and/or acute abdomen. Patients should be advised to report promptly any new or worsening abdominal pain or blood in their stools.

Renal Failure

Cases of rapidly progressive and sometimes fatal acute renal failure not clearly related to disease progression occurred in patients who received temsirolimus. Some of these cases were not responsive to dialysis.

Wound Healing Complications

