- Patients on temsirolimus will have serum chemistry and electrolytes including total protein, albumin, alkaline phosphatase, AST, ALT, calcium, LDH, total bilirubin, BUN, creatinine, phosphorus, glucose, sodium, potassium, chloride, and carbon dioxide will be done every 2 weeks for the first 8 weeks and every 4 weeks thereafter. Fasting lipid panel every 4 weeks for the first 8 weeks, every 8 weeks x 2, and every 16 weeks thereafter. CBC with platelet count and differential will be done every week for patients on temsirolimus.

- Record concomitant medications with each history and physical.
- Reconcile the medication diary provided during treatment with each history and physical for those on pazopanib.
- Adverse events will be assessed at each visit and monitored throughout the study.
- 12-Lead Electrocardiogram will be repeated at Cycle 2 Day 1, 12 weeks later, and every 16 weeks after that for patients on Pazopanib. (see Section 6.1.1.4 for additional details of QT interval monitoring) Patients receiving temsirolimus will have an ECG done every 16 weeks.
- Optional blood specimens for future correlative studies will be obtained every 8 weeks and at progression.
- Serum amylase and lipase will be obtained only as clinically indicated.
- Serum T4 and TSH will be obtained every 8 weeks for patients receiving pazopanib.
- Repeat radiological studies (CT, MRI as indicated) to evaluate response every 8 weeks. Studies to confirm a complete response or document progressive disease will be performed as needed. Patients who are progression free after 1 year can have their imaging studies obtained every 16 weeks.
- Echocardiogram or MUGA scan (echocardiogram preferred) will be repeated every 24 weeks and as clinically indicated.

Outside Physician Participation During Treatment (Temsirrolimus Patients may have interim infusions with local MD)

1. MDACC Physician communication with the outside physician is required prior to the patient returning to the local physician. This will be documented in the patient record
2. A letter to the local physician outlining the patient's participation in a clinical trial will request local physician agreement to supervise the patient's care (Appendix J); A copy of the protocol abstract and evaluation during treatment will be provided to the local physician with the letter.

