6.1.1.1 Guidelines for Management of Treatment Emergent Hepatotoxicity

In the event of treatment emergent hepatotoxicity, potential contributing factors such as concomitant medications, viral hepatitis, choledocholithiasis, and hepatic metastases should be investigated. Concomitant medications known to be hepatotoxic which may be contributing to liver dysfunction should be discontinued or replaced with alternative medications to allow for recovery of liver function. As generally understood, ALT $>3x$ ULN and concomitant bilirubin $\geq 2.0x$ ULN ($>35\%$ direct bilirubin), in the absence of elevated alkaline phosphatase or biliary injury, suggests significant liver injury. The table below provides guidelines for hepatotoxicity monitoring.

Event	Dose Modification Algorithms
(A). ALT $\leq 3.0 x$ ULN	Continue study treatment at current dose with LFTs monitored as per protocol.

(B). ALT >3.0 x ULN to ≤8.0 x ULN without bilirubin elevation (defined as total bilirubin <2.0 x ULN or direct bilirubin ≤35%) and without hypersensitivity symptoms (e.g., fever, rash)
	
Liver Event Monitoring Criteria:
 
(1) Continue study treatment at current dose levels.
 
(2) Monitor subject closely for clinical signs and symptoms; perform full panel LFTs once weekly or more frequently if clinically indicated until ALT/AST is reduced to Grade 1.

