9.0 STUDY CALENDAR

In the event that the patient's condition is deteriorating, laboratory evaluations should be repeated within 48 hours prior to initiation of the next cycle of therapy. All evaluations will have a standing window of allowance equal to +/- 3 days.

	Screening	Weekly	Every 4 Weeks	Every 8 Weeks	Every 16 Weeks	Off Treatment ^{q,r}
History & Physical Exam	x ^a		x ^p	x ^h		
Concomitant Meds	x ^a		x ^p	x ^h		x
Vital Signs incl. Weight	x ^a	x ^b	x ^p	x ^h		
Height	x ^a					
Performance Status	x ^a					
CBC w/ Dif & Plts.	x ^a	x ^{e,p}	x ^e	x ^e		
Serum Chemistry ^d	x ^a	x ^s	x ^s	x ^{h,s}	x ^{h,s}	
Lipid Panel	x ^a		x ^e	x ^e	x ^e	
Amylase	x ^{a, f}		x ^f			
Lipase	x ^{a, f}		x ^f			
PT/PTT	x ^a					
βHCG ^g	x ^a					
Free T4 & TSH ^h	x ^a			x ^h		
Urinalysis	x ^a			x ^{h,i}		
Radiological Evaluation ^j	x ^k			x	x ^t	
Electrocardiogram	x ^k		x ^{f,n}		x ^p	
Echocardiogram or MUGA scan	x ^m		Repeated every 24 weeks			
	Screening	Every 8 weeks off treatment				
Adverse Event Monitoring		Adverse Events will be monitored throughout				
Quality of Life battery	x ^a			x		
Optional Blood Collection ^l	x ^a			x		x

Optional Tissue Collection ^{c,o}	
---	--

- a. Within 14 days of registration
- b. Only the blood pressure must be monitored weekly for the 1st 4 weeks on study in patients receiving pazopanib. This may be performed at a doctor's office or using any calibrated electronic device.
- c. Previously collected tissue, will be requested from patients who consent. This tissue may come from MD Anderson or an outside institution. Tissue will be requested, once the study is closed to new patient entry, to allow for batch analysis. No new procedures will be required. This tissue will also be banked for future research related to immunologic response.
- d. Serum chemistry consists of total protein, albumin, alkaline phosphatase, AST and ALT, calcium, LDH, total bilirubin, BUN, creatinine, phosphorus, glucose, sodium, potassium, chloride, carbon dioxide.
- e. CBC with platelet count and differential will be done every 2 weeks for the first 8 weeks, every 8 weeks x 2, and every 16 weeks thereafter, for patients on pazopanib. For patients on temsirolimus, a CBC with platelet count and differential will be done weekly. Fasting lipid panel will be done every 4 weeks for the first 8 weeks, every 8 weeks x 2, and every 16 weeks thereafter, for those patients receiving temsirolimus.
- f. As clinically indicated

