- g. Female patients of child-bearing age must have a negative pregnancy test within 7 days of beginning treatment.
- h. Patients receiving pazopanib only
- i. Urinalysis. If patient has urine protein ≥ 300 on UA, a random UPC ratio should be ordered.
- j. CT Chest, abdomen and pelvis. MRI of the brain (bone scan, plain films) should be obtained as appropriate. MRI of the abdomen and/or CT scan of the brain can be substituted at the physician's discretion.
- k. Within 4 weeks of study entry
- l. Optional blood collection for future correlative studies will be drawn at baseline, every 8 weeks, and at Off Treatment Visit.
- m. Within 12 weeks of study entry
- n. Patients receiving pazopanib will have a follow-up ECG at C2D1, 12 weeks later, and every 16 weeks thereafter.
- o. Tissue will also be collected during procedures performed, at any time point, while patients are enrolled in this study. No new procedures will be required. This tissue will also be banked for future research related to immunologic response.
- p. Patients receiving temsirolimus
- q. In 30 days after stopping therapy
- r. Long-Term Follow-Up for survival will occur every 3 months from final study therapy. Follow-up will consist of a phone call, e-mail correspondence or medical record review.
- s. Every 2 weeks for the first 8 weeks (both arms). Temsirolimus patients every 4 weeks thereafter. Pazopanib patients every 8 weeks x 2 and every 16 weeks thereafter.
- t. Patients who are progression free after 1 year can have their imaging studies obtained every 16 weeks.

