Where HR is the hazard ratio (experimental:control). For sample size calculation purposes we assume that the median PFS in the temsirolimus arm is 60% that of the pazopanib arm (3.8 months versus 6.1 months). The sample size estimate is based on a one-sided log-rank test with type one error equal to 0.10 and power of 0.80.

We will conduct an interim analysis for futility after 42 events have been observed. If the p-value used to assess futility at the interim analysis is greater than 0.4798 we will stop the trial early for futility.

Secondary Objectives

Overall survival: Overall survival is calculated from day of therapy initiation to the date of death. Patients who are lost to follow-up will be censored at date of last contact.

We will use the Kaplan-Meier estimator to estimate the OS for each group of patients (control, experimental), and the log-rank statistic will be used to test for treatment differences. We will also use the Cox proportional hazards regression model to estimate the hazard ratio (experimental:control) for OS with a 95% confidence interval.

We will also assess the response rate and report 95% confidence intervals.

Additional analyses:

Demographics

For each treatment group (control, experimental), summary statistics will be provided for age, weight, baseline disease status and prior treatments.

Toxicities

Toxicities and side effects that will be evaluated include, but are not limited to infections, renal toxicity, hepatic toxicity, and pulmonary toxicity. Methods of assessment will include monitoring blood counts, and performing laboratory tests as indicated by clinical signs and symptoms. Evidence of toxicities or adverse events will be recorded at all clinic visits. All observed toxicities and side effects will be graded (NCI CTC-AE v. 4.0) for all patients and the degree of association of each with pazopanib or temsirolimus assessed. The incidence and severity of toxicities will be compared between the two treatment arms with Fisher's exact test.

Stratification Factors

The Pocock-Simon Minimization Method will be used to randomize patients according to the following stratification factors:

- Prior nephrectomy status (yes or no)
- Prior cytokine/vaccine therapy (yes or no)

The randomization program based on this method will be developed in the Department of Biostatistics and Applied Mathematics, and the program will be available via an intranet web site of MD Anderson Cancer Center.

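### The planned between-arm Fisher tests cannot separate drug from testing schedule for lipid and thyroid toxicities, and can mildly mislead for brief, silent cytopenias; a minor, cheap fix to the analysis

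*Combined protocol and SAP*

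**What the plan says.** Under Toxicities, section 13.0 plans: "The incidence and severity of toxicities will be compared between the two treatment arms with" Fisher's exact test. The list of toxicities is open-ended, and laboratory work beyond blood counts is left to clinical signs and symptoms. Sections 13 and 14 do not mention unequal testing, common time points or a denominator of patients tested. Section 14.1 makes both treatment stages evaluable for toxicity without saying which stage the test uses.

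The schedules differ by arm:

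- **Lipids** (section 9.0, footnote e): every 4 weeks for the first 8 weeks, then "every 8 weeks x 2, and every 16 weeks thereafter, for those patients receiving temsirolimus". No on-treatment lipid panel is scheduled on pazopanib.
- **Thyroid** (section 5.4): "Serum T4 and TSH will be obtained every 8 weeks for patients receiving pazopanib". None is scheduled on temsirolimus.
- **Blood counts** (section 9.0, footnote e): one arm is sampled "every 2 weeks for the first 8 weeks, every 8 weeks x 2, and every 16 weeks thereafter, for patients on pazopanib". The same footnote sets a much denser schedule in the other arm: "For patients on temsirolimus, a CBC with platelet count and differential will be done weekly".
- **Chemistry** (section 9.0, footnote s): "Every 2 weeks for the first 8 weeks (both arms). Temsirolimus patients every 4 weeks thereafter". Pazopanib then moves to every 8 weeks twice and every 16 weeks after that.

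Section 5.3.1 measures lipids and thyroid function in both arms at screening, so the imbalance begins on treatment.

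**The concern.** Fisher's test compares the proportions of patients in whom a toxicity was recorded. A laboratory toxicity without symptoms is recorded only if someone takes the sample. Where one arm is sampled by schedule and the other only on suspicion, the arms can differ even if the drugs do not. Where both are sampled but one more often, short episodes are caught more often in the more frequently sampled arm.

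Safety is a secondary objective in section 1.0, and the plan chose an inferential test for it. At stake is a published p-value for lipid or thyroid events that reflects who was sampled, and possibly an apparent excess of cytopenia on temsirolimus that comes from weekly counts.

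**Working it through.** **The plan's own figures.** The documents give no power or error rate for the toxicity comparison, so there is none to reproduce. The planning figures used are 45 per arm, the general two-sided 0.05 level, and median PFS of 3.8 v 6.1 months (section 13.0). The PFS sizing is coherent: HR = 3.8/6.1 = 0.623, and 4 × (1.2816 + 0.8416)² / (ln 0.623)² gives 81 events, which fits within 90 patients.

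**Scheduled on-treatment tests by week 24**

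| Test | Temsirolimus | Pazopanib |
|---|---|---|
| Lipids | 4 (weeks 4, 8, 16, 24) | 0 |
| T4/TSH | 0 | 3 (weeks 8, 16, 24) |
| CBC | 24 (weekly) | 6 (weeks 2, 4, 6, 8, 16, 24) |
| Chemistry | 8 | 6 |

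To allow for drop-out, take exponential time on treatment with the PFS medians: 3.8 × 30.4375/7 = 16.5 weeks and 6.1 × 30.4375/7 = 26.5 weeks. Summing 0.5^(t/median) over the CBC weeks gives 14.8 v 4.7 expected counts per patient.

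**Rejection probability.** For detected incidences p₁ and p₂, sum Bin(a; 45, p₁) × Bin(b; 45, p₂) over all pairs (a, b) whose two-sided Fisher p is at most 0.05. For scale, 6 of 45 against 0 of 45 gives p = 0.026, and 5 against 0 gives p = 0.056.

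**Parameters scheduled in one arm only.** Let the true incidence p be equal in both arms, and let q be the share of the unscheduled arm that is tested anyway. Then p₁ = p and p₂ = p × q. With drop-out, p₁ is multiplied by the share still on treatment at the first scheduled test: 0.5^(4/16.5) = 0.846 for lipids and 0.5^(8/26.5) = 0.811 for T4/TSH. Each range runs from p = 20% to p = 40%.

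| q | No drop-out | Lipids, drop-out | T4/TSH, drop-out |
|---|---|---|---|
| 0 | 91-100% | 80-100% | 76-100% |
| 10% | 73-99% | 57-96% | 53-94% |
| 25% | 48-89% | 32-72% | 29-67% |
| 50% | 18-46% | 10-24% | 8-19% |

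**Blood counts.** Assume one silent episode per affected patient, onset uniform over 24 weeks, scheduled tests only, and equal true incidence of 20-40%. Detected shares are temsirolimus v pazopanib.

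| Episode length | Detected, all followed to week 24 | Rejects | Detected, planning medians | Rejects |
|---|---|---|---|---|
| 1 week | 100% v 25% | 48-89% | 62% v 20% | 17-49% |
| 2 weeks | 100% v 50% | 18-46% | 62% v 39% | 5-12% |
| 4 weeks | 100% v 67% | 8-21% | 62% v 49% | 3-5% |
| 8 weeks | 100% v 100% | about 3% | 62% v 69% | 3-4% |

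These are exact sums; simulation can differ by about one percentage point (6-13% for 2-week episodes). The planning-median columns are the relevant ones: at those medians only 0.5^(24/16.5) = 37% of temsirolimus patients and 0.5^(24/26.5) = 53% of pazopanib patients would still be on treatment at week 24.

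**Can the common weeks settle it?** Restricting both arms to the shared CBC weeks brings rejection under equal incidence down to 0.3-5%, at a price in power. For a real 40% v 10% excess on temsirolimus at the planning medians, power falls from 0.90 to 0.04 (1-week episodes), 0.77 to 0.23 (2-week), 0.70 to 0.32 (4-week) and 0.55 to 0.46 (8-week). The common weeks also do not expose a false excess. Among simulated trials with a false significant excess on temsirolimus, the direction is the same at the common weeks in about 61-78% (1-week), 93-98% (2-week) and 99-100% (4-week). Every scheduled pazopanib count is already a common-week count, so the same low pazopanib number is used twice.

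**The case against.** The strongest case against acting has four parts.

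- **Toxicity testing is peripheral.** It sits under additional analyses. The four toxicities named there (infections, renal, hepatic, pulmonary) include no lipid, thyroid or blood-count item. This stands as a limit on importance. The list is expressly open, though, and all observed toxicities are graded, so lipid and thyroid events can enter the test.
- **Different drugs call for different monitoring, and lipid rises are expected on temsirolimus.** Both are true. The point is not that the schedules are wrong or that the drugs are alike. It is that the test would look much the same whether or not they are.
- **The blood-count effect is narrow.** This stands. At the planning medians, material inflation needs silent episodes of about one to two weeks, and the documents give no durations. Symptom-driven tests and repeat counts during a dose hold would shrink it further.
- **Recorded toxicities are not raw laboratory flags.** This stands. In the section 11.0 recording table for phase II, grade 1-2 events judged unrelated or unlikely are not captured.

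A reader might go further and take the section 3.2.5 figures ("87% of patients receiving temsirolimus had at least one elevated serum cholesterol value and 83% had at least one elevated serum triglyceride value") as the toxicity rate, which would make a false difference look close to certain. The documents do not support that. These are rates of any elevated value, and the same section shows how far the two can differ: for glucose, 89% had an elevated value but 26% had hyperglycemia reported as an adverse event. The 83% scenario is therefore not used.

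A reader might also extend the concern to liver and renal toxicity. Scheduled chemistry is nearly balanced (4 v 4 by week 8, 8 v 6 by week 24). Section 6.1.1.1 does add tests on pazopanib after an ALT rise ("perform full panel LFTs once weekly or more frequently if clinically indicated until ALT/AST is reduced to Grade 1"), which could affect the recorded peak grade, but that does not make the comparison one of tested against untested patients.

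**Conclusion.** The point holds, as a minor one. For lipid and thyroid toxicities the planned test cannot distinguish a drug effect from the schedule. Under equal true incidence of 20-40% it rejects far above 5% unless a large share of the unscheduled arm is tested anyway; with half tested and drop-out allowed for, it still rejects in 10-24% (lipids) and 8-19% (T4/TSH). For blood counts the risk is a false excess on temsirolimus of limited reach: about 17-49% for 1-week and 5-12% for 2-week silent episodes at the planning medians, with little or no inflation at 4 weeks or longer.

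Incidence, episode duration, onset pattern and unscheduled-testing rates are assumptions, because the documents give none. The sums also take treatment time as equal to PFS and use first-line data only.

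It might be inferred that the trial's safety conclusions as a whole are unsound, or that a blood-count difference which keeps its direction at the common weeks must be a drug effect. Neither follows. The first overlooks the near-balanced chemistry; the second fails on the persistence figures above. No efficacy conclusion or stopping rule depends on these tests.

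**What to change.** Change the analysis text only; monitoring and care stay as written.

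1. Report lipid and thyroid toxicities descriptively by arm, with the number of patients tested on treatment, and no between-arm Fisher test.
2. Keep the planned Fisher test for haematological toxicities. Beside it, report the number of CBCs per patient by arm and, as a descriptive sensitivity analysis, incidence at the common weeks (2, 4, 6, 8, 16, 24, then every 16 weeks). State its low power for short episodes. Do not use persistence of direction or risk ratio as a rule for attributing a difference to the drug.
3. State that the between-arm test uses first-line toxicity, with second-stage toxicity reported separately by drug.

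The cost is a few sentences and one extra table, with no new data. The downside is that lipid and thyroid events carry no p-value.

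Three texts should be reconciled at the same time, although the point does not rest on them: the arm to which urinalysis applies (section 5.4 is ambiguous, the calendar marks it for pazopanib only); the pazopanib ECG schedule (section 5.4 and calendar footnote n against section 6.1.1.4); and the visit window (±7 days in section 5.4, ±3 days in section 9.0), which also determines which counts belong to a common week.

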5.9 Duration of Therapy

Patients may continue therapy until progressive disease by RECIST criteria or until other criteria for removal (Section 12) has been met.

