13.0 STATISTICAL CONSIDERATIONS

This is a randomized, two-arm, parallel group, phase II trial enrolling advanced, poor-risk, clear-cell RCC. Patients will be fairly randomized to either temsirolimus (control arm) or pazopanib (experimental arm).

The maximum sample size to be accrued is 90 patients (45 in each treatment arm). The primary measure of efficacy and primary endpoint is progression free survival (PFS). PFS will be monitored on an interim basis and we will use stopping rules for futility to serve as guidelines for early termination. The stopping rules are ad-hoc in nature but are selected in a manner such that the overall type 1 error is controlled at a one-sided 10% with 80% power.

Descriptive and inferential statistics will be used to summarize treatment effects. The mean, standard deviation, median, 25% percentile, 75% percentile, minimum, and maximum will be reported for continuous variables. For discrete variables, descriptive analyses will be based on the distribution of discrete outcomes and will be reported as percentages and patient counts. Time to event endpoints will be descriptively summarized by Kaplan-Meier curves. Point and interval estimates of treatment effect will be based on maximum likelihood methods. For binomially distributed variables, we will report differences in proportions between treatment groups and the 95% confidence interval associated with those differences. We will estimate treatment effects for time to event variables via hazard ratios using Wald scores from Cox proportional hazard regression models. Unless stated otherwise, all statistical tests will be assessed using a two-sided $\alpha = 0.05$ alpha significance level and confidence intervals will be constructed using two-sided 95% and will be based on the normal approximation. Although multiple secondary endpoints will be evaluated we will make no adjustment for multiplicities associated with these multiple tests.

Estimation of Sample Size

The clinical hypothesis we are assessing in this trial is whether patients receiving the experimental therapy have a lower hazard of progression or death relative to patients receiving the control therapy. The statistical hypothesis is stated as:

$$H_0: \log(HR)=0$$

$$H_A: \log(HR)<0$$

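### If PFS is longer on pazopanib as the design assumes, the crude Fisher comparison of toxicity leans against pazopanib for events that keep arising during treatment

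*Combined protocol and SAP*

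**What the plan says.** Safety is a secondary objective (section 1.0). Under Toxicities, section 13.0 states: "The incidence and severity of toxicities will be compared between the two treatment arms" by Fisher's exact test. Discrete outcomes "will be reported as percentages and patient counts", differences in proportions get 95% confidence intervals, and by default "all statistical tests will be assessed using a two-sided" 5% level. No toxicity analysis uses person-time, time to first event or a common time window.

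On time on drug, section 5.9 says: "Patients may continue therapy until progressive disease by RECIST criteria", or until a removal criterion is met. Section 5.2 gives both drugs until progression, prohibitive toxicity or withdrawal of consent. For the sample size, section 13.0 assumes that "the median PFS in the temsirolimus arm is 60% that of the pazopanib arm (3.8 months versus 6.1 months").

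Patients may cross over at progression (sections 5.1 and 5.6). Section 14.1 makes them evaluable for toxicity in both stages, without saying which stage enters the between-arm test.

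**The concern.** A patient who stays on a drug longer has more time in which to have a first event. With treatment to progression, an arm with longer PFS accumulates a higher proportion of patients who ever had the event, even when the risk per month on drug is the same in both arms. Fisher's test on that proportion cannot separate a more toxic drug from a drug taken for longer.

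What is at stake is the benefit-risk reading in the scenario the trial hopes for. If pazopanib delays progression, part of its apparent extra toxicity would be a by-product of that delay. The difference in proportions would be reported whether or not the test is significant. The primary PFS test is unaffected.

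**Working it through.** **Inputs.** Section 13.0: 45 patients per arm, two-sided 5% for toxicity tests, medians 3.8 and 6.1 months. The plan gives no toxicity planning rates and no onset pattern, so monthly hazards of 0.03 to 0.30 are an assumption, shown as a range. Time on drug is taken as equal to PFS. There is some support for this: sections 2.3 and 3.2.3 report, for temsirolimus in the earlier phase 3 trial, a median PFS of 3.8 months and a median treatment duration of 17 weeks (17 × 7 / 30.4375 = 3.9 months).

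**The plan's own figures.** The toxicity comparison has no stated operating characteristics, so the check is on the PFS design that supplies the medians: "one-sided log-rank test with type one error equal to 0.10 and power of 0.80".

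- Hazard ratio: 3.8/6.1 = 0.623. Ratio of medians: 6.1/3.8 = 1.605.
- Schoenfeld: 4(1.2816 + 0.8416)² / (ln 0.623)² = 18.03/0.224 = 80.5, so 81 events.
- Freedman: (1.623/0.377)² × 4.508 = 83.5, so 84 events. The 42-event interim analysis is half of 84.

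Both counts fit within 90 patients, so the design reproduces on these medians. The final event count is not stated, and 84 is inferred.

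**Case 1: equal, constant hazard λ while on drug.** With exponential time on drug, the probability of ever having the event is λ/(λ+μ). Here μ = ln 2/3.8 = 0.1824 for temsirolimus and ln 2/6.1 = 0.1136 for pazopanib (mean times 5.5 and 8.8 months). Fisher rejection probabilities are by full enumeration of two binomials with n = 45.

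| λ per month | Temsirolimus | Pazopanib | Excess (points) | Fisher rejects |
|---|---|---|---|---|
| 0.03 | 14.1% | 20.9% | 6.8 | 8% |
| 0.10 | 35.4% | 46.8% | 11.4 | 14% |
| 0.15 | 45.1% | 56.9% | 11.8 | 14% |
| 0.30 | 62.2% | 72.5% | 10.3 | 13% |

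At 0.10 per month the rejection probability is 13.9%, nearly all of it against pazopanib, and pazopanib has the numerically higher count in 84% of trials. With equal exposure at the temsirolimus incidence, Fisher's test rejects in about 3%. Adding a one-month window after the last dose in both arms, for temsirolimus incidences of 10% to 70%, gives an excess of 4 to 10 points and rejection of 5% to 11%.

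**Case 2: equal hazard, early treatment only.** If the hazard acts only in the first W months, the probability is λ/(λ+μ) × [1 − exp(−(λ+μ)W)].

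| W (months) | λ per month | Temsirolimus | Pazopanib | Excess (points) |
|---|---|---|---|---|
| 1 | 0.10 | 8.7% | 9.0% | 0.3 |
| 1 | 0.30 | 23.8% | 24.6% | 0.8 |
| 2 | 0.10 | 15.3% | 16.3% | 1.0 |
| 2 | 0.30 | 38.5% | 40.8% | 2.3 |

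Rejection in these four rows stays between about 2% and 3.5%, so the bias is small.

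**Case 3: common 16-week window.** W = 16 × 7 / 30.4375 = 3.68 months. At λ = 0.10:

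- temsirolimus: 0.3541 × [1 − exp(−0.2824 × 3.68)] = 22.9%
- pazopanib: 0.4681 × [1 − exp(−0.2136 × 3.68)] = 25.5%

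The residual excess is 2.6 points and Fisher's test rejects in 3.3%.

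**Two tempting remedies.**

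- *Events per patient-month.* Under constant hazard this works: rate ratio about 1.01, rejection 4.7% to 5.1%. It fails for early-onset events. With a month-1-only hazard of 0.10 and all first-line time in the denominator, the pazopanib:temsirolimus ratio is (0.0900/8.80) / (0.0871/5.48) = 0.64. With the hazard confined to the first four months it is (0.2689/8.80) / (0.2397/5.48) = 0.70. Two equally toxic drugs would show pazopanib as 30% to 36% less toxic.
- *Competing-risk cumulative incidence.* With stopping drug as the competing event, the curve rises to λ/(λ+μ), which is the same 35% v 47% at 0.10 per month.

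**The case against.** The strongest reply is that a reader might infer that two equally toxic drugs would show a spurious pazopanib excess in this trial. The documents do not support that. The 3.8 and 6.1 month medians are a sample-size assumption; with equal PFS there is no exposure gap. The documents give no onset times, and for early toxicity the excess nearly vanishes. Even in the constant-hazard model about 86% of trials show no significant difference. All of this stands and limits the point to a conditional one.

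The direction is also not fixed under the plan as written. If second-stage events count by randomised arm, exposure to the two drugs is mixed. Section 5.4 has weekly blood counts on temsirolimus, against every 2 weeks for 8 weeks and then every 8 and 16 weeks on pazopanib. It also has examinations every 4 weeks against every 8. For laboratory toxicity that pushes the other way. The size of this detection effect is unknown, so it cannot be relied on to cancel the exposure effect.

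Time on drug need not equal PFS either: toxicity can end treatment earlier, and section 5.6 allows the first agent to continue after RECIST progression.

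Finally, whole-course incidence answers a fair question: the chance of a toxicity over a course given until progression. That justifies reporting it. It does not justify making it the only comparison, because readers will take a difference as a property of the drug.

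**Conclusion.** The point holds in conditional form. If PFS is longer on pazopanib as designed, and for toxicities that keep arising on treatment, the planned comparison is biased toward more pazopanib toxicity. The size is about 7 to 12 points in expected incidence. Rejection at 45 per arm is 8% to 14% per toxicity, against about 3% with equal exposure.

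This rests on exponential time on drug equal to PFS, the same constant hazard of 0.03 to 0.30 per month in both arms, and first-line events only. For toxicity confined to the first month or two the bias is about 0 to 2 points. The main effect is a shifted estimate. The figures do not support a reading that a significant spurious result is likely, or that all of pazopanib's observed toxicity excess would be an artefact.

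**What to change.** In section 13.0:

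- Limit the between-arm toxicity comparison to the first-line, pre-crossover period, and say how second-stage events are reported.
- Compare arms on time to first event of each toxicity by a cause-specific log-rank or Cox analysis, censoring at the end of first-line drug plus any fixed safety window.
- Keep Fisher's test for a common early window, for example the first 16 weeks.
- Show crude whole-course incidence as description only.
- Do not use simple events per patient-month as the comparison, and do not rely on competing-risk cumulative incidence to remove the gap.

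The cost is SAP wording and a little more analysis, with no change to sample size, visits or treatment. It needs onset dates for adverse events. Section 13.0 says only that events are recorded at all clinic visits, so that the dates are held is an assumption to confirm. Onset times will be coarse where laboratory visits are sparse, mainly later on pazopanib, and the analysis does not correct for unequal testing between arms.
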